7.4.3 Dose Escalation/De-escalation

Enrollment will be temporarily suspended after every 5 participants to evaluate phospho-EGFR response. If all 5 participants are evaluable, the dose level has been deemed safe, and phospho-EGFR is inhibited (i.e., a response, see Section 13) in at least 40% of evaluable participants, then enrollment will

continue at the next lower dose. If there are < 5 evaluable based on phospho-EGFR staining and the DLTs are below the limits specified above, then 5 more will be enrolled at that dose level in an attempt to reach a total of at least 5 evaluable participants. If the total number of evaluable participants remains < 5 and the dose level is deemed safe, then 5 more participants will be enrolled at this same dose level.

At dose level 0, if fewer than 2 responses are observed (in the first 5 evaluable participants) and the dose level is deemed to be safe, 15 participants will be enrolled at the next higher dose level (+1). If at least 2 participants have a response in the first 5 evaluable at this dose level and the dose level is deemed to be safe, this dose level will be declared the MED and further study with this dose will be warranted. If fewer than 2 responses (in the first 5 evaluable) are observed at this dose level, 15 participants will be enrolled at the next higher dose level (+2). If at least 2 responses are observed (in the first 5 evaluable participants) at this dose level and the dose level is deemed to be safe, this dose level will be declared the MED and further study with this dose will be warranted. If fewer than 2 responses are observed at this dose level (in the first 5 evaluable participants), we may consider including additional dose levels, after discussion with the DCP medical monitor, to find the MED for this study.

The lowest dose level at which there are ≥ 5 participants and $\geq 40\%$ of these evaluable participants demonstrate a phospho-EGFR response will be considered the minimum effective dose (MED).

Reopening to enrollment after a temporary closure will occur after consultation with the DCP medical monitor.

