7.7 Methods for Clinical Procedures

7.7.1 Pre-intervention

After informed consent and screening, and prior to initiation of erlotinib treatment, all surgical cohort participants will undergo a percutaneous or transjugular biopsy of their cirrhotic/fibrotic liver in a non-tumor bearing area. Participants should remain NPO after midnight before the scheduled biopsy to allow for use of conscious sedation if indicated. Whether to perform the biopsy under local anesthesia or under conscious sedation will be at the discretion of the clinician performing the biopsy. For percutaneous biopsy a 16-gauge core is preferable; an 18-gauge core is acceptable. All participants will be monitored post-procedure according to institutional standards of good clinical practice, after which time they may be discharged to home. The biopsy may be conducted via transjugular approach or under ultrasound guidance as deemed appropriate and will consist of 4 samples, of which 2 will be placed in RNAlater (Qiagen), and two will be placed in formalin. All samples will be stored in a refrigerator. If the clinician performing a percutaneous biopsy is unable to obtain at least two (2) core biopsies safely (e.g. participant starts bleeding), the clinician should abort the attempt. The participant will be considered not evaluable.

After informed consent, specimens will be obtained from clinically-indicated liver biopsy for all non-surgical cohort participants. Formalin blocks or unstained slides will be obtained and submitted to the CPN Pathology Coordinator for accessioning. The Pathology Coordinator will submit them to Mayo Clinic Pathology Research Core (PRC) for phospho-EGFR assessment.

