7.7.2 Post-Intervention

For surgical cohort participants, liver resection surgery and post-surgical observation should follow institutional standards of care and good clinical practice. After liver resection, a portion of the liver specimen that does not contain tumor and consists of at least 1 gram of liver tissue will be placed in RNAlater (Qiagen). One other section of non-tumor bearing liver tissue measuring at least 1 cm x 1 cm x 0.5 cm will be placed in formalin and stored in the refrigerator.

Non-surgical cohort participants will undergo a post-intervention percutaneous or transjugular biopsy of their cirrhotic/fibrotic liver in a non-tumor bearing area. Participants should remain NPO after midnight before the scheduled biopsy to allow for use of conscious sedation if indicated. Whether to perform the biopsy under local anesthesia or under conscious sedation will be at the discretion of the clinician performing the biopsy. For percutaneous biopsies, a 16-gauge core is preferable; an 18-gauge core is acceptable. All participants will be monitored post-procedure according to institutional standards of good clinical practice, after which time they may be discharged to home. Percutaneous biopsy may be conducted under ultrasound guidance. Whether by percutaneous or transjugular approach, biopsies will consist of a minimum of 2 samples. Four (4) samples is preferable. The first two samples will be placed in formalin. The second two will be placed in RNAlater (Qiagen). The four samples will be stored in a refrigerator. If the clinician performing a percutaneous biopsy is unable to obtain the first two core biopsies safely (e.g. participant starts bleeding), the clinician should abort the attempt. The participant will be considered not evaluable.

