If multiple specimens from a single participant are analyzed, the specimens showing the most significant reduction in percentage of positive pixels in response to erlotinib will be used for analysis. The rationale is that this pilot study is looking for evidence of a signal (i.e. a reduction in phospho-EGFR staining that indicates an effect on the pathway).

- Cell lines and/or tissue that are positive and negative for phospho-EGFR will serve as a positive and negative control.
- Allowable formalin fixation time for needle biopsy specimens: 4 to 24 hours
- Allowable formalin fixation time for resected liver specimens: 24 to 48 hours.
- All sections for staining should be cut at 10 microns.

In the nonsurgical cohort, positive **phospho**-EGFR assessment for initial eligibility will be defined as a minimum of 100 stained pixels.

For the immunohistochemical staining of paraffin-embedded liver tissues, the following antibodies will be used: phospho-EGFR:

- Cell Signaling - #2236 (mouse monoclonal). This detects phosphorylation at Tyr1068.
- phospho-ERK: Cell Signaling - #9101 (rabbit polyclonal) - which detects phosphorylation at Thr202/Tyr204
- PCNA: Cell Signaling - #2586 (mouse monoclonal)
- EGF: R&D Systems - #MAB236 (mouse monoclonal)
- α SMA: DakoCytomation #M0851 (mouse monoclonal). An alternative that has also been successful is Abcam #ab5694 (a rabbit polyclonal), which will be employed if necessary.

Note: Heavier or darker staining is commonly seen along the edges of IHC stained tissue sections. This is an artifact in the staining. Under the guidance of an Anatomic Pathologist, this artifact is avoided in selecting the analysis region for each slide.

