10.2.2.4 Non-Surgical Cohort – Post-Intervention

The post-intervention percutaneous or transjugular liver biopsy may be conducted following institutional standards of care before, during, and after the procedures. The collected specimens will consist of 4 samples. Two will be placed in RNAlater (Qiagen), and the other two will be placed in formalin. All specimens will be clearly labeled with study number, participant ID, specimen type, and date and time of collection. The RNAlater samples will be stored in a refrigerator at the participating sites until shipped to the BAP Lab. The BAP Lab will store samples in a -80°C freezer until sent to [name] lab (upon request).

The fresh formalin samples will be embedded in paraffin within 24 hours. The date and time of collection as well as paraffin embedding will be recorded on the Specimen Submission: Tissue case report form. Paraffin blocks will be shipped refrigerated to the Mayo Clinic (CPN PC Office, address below) for accessioning.

At the same time, the paraffin block containing the specimen used to establish initial eligibility at baseline will be submitted to the CPN PC Office. Additional sections are required because it is critical

that specimens used for efficacy analysis at the end of each dose level be cut for both time points and for all participants at the same time.

Institutions unable to submit paraffin blocks may submit one 3.0mm to 4.0mm core taken from each block and placed into individual 2mL tubes. If cores cannot be provided, cut one H&E and 10 sections at 5 microns and mount on charged slides.

Notes:

- For institutions that must, per institutional policies, provide cores or slides instead of paraffin blocks: **Do not create the cores or cut slides until requested to do so by the CPN Pathology Coordinator.** Analysis for the study endpoints requires all slides for both time points for all participants to be sectioned at the same time.
- **Note: Sites are to notify CPN Pathology Coordinator ([name]; [contact]; [contact]) when specimens are shipped for tracking purposes.**

Post-intervention paraffin blocks (or cores) will be shipped from the CPN PC Office to the PRC at the Mayo Clinic in the same batch as the pre-intervention specimens at the conclusion of enrollment for each dose level.

Shipping Destination Summary:

Pre- and post-intervention paraffin blocks (or cores or unstained and H&E slides) will be shipped from all participating sites to:

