13.8 Evaluation of Response

Minimal Effective Dose (MED) determination (using dose levels defined in section 5.1)

In addition to assessment of responses discussed below, the dose-escalation/de-escalation decision will also depend on safety, see Section 7.3.

Ten participants will be enrolled at the starting dose level (dose level 0) and if at least 2 in the first 5 evaluable participants have a response (40%) and the dose level is deemed to be safe, 10 participants will be enrolled at the next lower dose level (-1). If at least 2 participants have a response in the first 5 evaluable at this dose level and this dose level is deemed to be safe, 10 participants will be enrolled at the next lower dose level (-2). If at least 2 responses are observed at this dose level as well (in the first 5 evaluable) and this dose level is deemed to be safe, then this dose level will be considered the observed MED for this study, and further study will be warranted at this dose level.

At dose level 0, if fewer than 2 responses are observed (in the first 5 evaluable participants) and the dose level is deemed to be safe, 10 participants will be enrolled at the next higher dose level (+1). If at least 2 participants have a response in the first 5 evaluable at this dose level and the dose level is deemed to be safe, this dose level will be declared the MED and further study with this dose will be warranted. If fewer than 2 responses (in the first 5 evaluable) are observed at this dose level, 10 participants will be enrolled at the next higher dose level (+2). If at least 2 responses are observed (in the first 5 evaluable participants) at this dose level and the dose level is deemed to be safe, this dose

level will be declared the MED and further study with this dose will be warranted. If fewer than 2 responses are observed at this dose level (in the first 5 evaluable participants), we may consider including additional dose levels to find the MED for this study.

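### Scoring each participant on the specimen with the largest phospho-EGFR drop raises the chance that a dose passes the 2-of-5 response rule and inflates the expansion response rate

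*Combined protocol and SAP*

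**What the plan says.** The rule is in Section 9.1, in the account of phospho-EGFR staining. It is conditional: "If multiple specimens from a single participant are analyzed", then "the specimens showing the most significant reduction in percentage of positive pixels in response to erlotinib will be used for analysis". The reason offered is "The rationale is that this pilot study is looking for evidence of a signal".

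The percentage of positive pixels is the primary endpoint measure (Sections 1.1, 8.1 and 13.4). A response is a fall of at least 50% from baseline. Section 13.8 moves down a dose "if at least 2 in the first 5 evaluable participants have a response (40%) and the dose level is deemed to be safe", and Section 7.4.3 defines the MED from the same response. Sections 8.1, 13.4, 13.6 and 13.8 contain no other rule for choosing or combining specimens.

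The sampling plan supplies more than one formalin specimen at one time point in each cohort:

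- **Surgical cohort, baseline** (Section 7.7.1): the biopsy "will consist of 4 samples, of which 2 will be placed in RNAlater (Qiagen), and two will be placed in formalin".
- **Surgical cohort, after treatment** (Section 7.7.2): "One other section of non-tumor bearing liver tissue measuring at least 1 cm x 1 cm x 0.5 cm will be placed in formalin".
- **Non-surgical cohort, baseline** (Section 10.2.2.3): tissue from one earlier clinical biopsy.
- **Non-surgical cohort, after treatment** (Section 10.2.2.4): "Two will be placed in RNAlater (Qiagen), and the other two will be placed in formalin".

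The documents do not say how many of these specimens will be stained and scored.

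**The concern.** Choosing a specimen by its outcome and then testing that outcome against a threshold biases the result in one direction. The largest reduction over the candidate pairs is never smaller than the reduction in a pair fixed in advance. Nor is it smaller than the pooled reduction, because a pooled pixel ratio lies between the two core ratios.

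Subject to the safety rule, the 2-of-5 response rule decides every move between doses. Extra false responses carry a step-down search further and stop a step-up search sooner, so both routes favour too low a dose. Section 2.3 gives finding the lowest dose that effectively inhibits EGFR in the liver as the reason for the trial. The expansion response rate, which Section 13.4 intends for planning a larger study, is scored the same way.

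Looking for a signal could justify an exploratory display. It does not fit a thresholded dose decision or a response-rate estimate.

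**Working it through.** **1. The plan's own figures.** With X ~ Binomial(5, 0.6), P(X ≥ 2) = 1 − 0.010 − 0.077 = 0.913, which matches the 91% in Section 13.4. The 90% margin with 10 evaluable is 1.645 × √(0.6 × 0.4 / 10) = 0.255, which matches the stated margin of about 25%. Neither figure allows for specimen selection, and no pass probability is given for an inactive or weak dose.

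**2. Candidate pairs.** If both cores are scored, the surgical cohort has 2 baseline × 1 post = 2 pairs and the non-surgical cohort 1 × 2 = 2 pairs.

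**3. Model (assumed).** Specimen values are log-normal with log-scale SD s, so CV = √(exp(s²) − 1). Cores from one time point have correlation r on the log scale. A response is post ≤ 0.5 × pre. Three scorings are compared: cores pooled (equal areas), one pair fixed in advance, and the best pair. Passing is P(X ≥ 2) with X ~ Binomial(5, p).

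For a fixed pair with no drug effect, p = Φ(ln 0.5 / (s√2)). At s = 0.4 (CV 42%) this is Φ(−1.225) = 0.110, and P(pass) = 1 − 0.890⁵ − 5 × 0.110 × 0.890⁴ ≈ 0.10. The best pair raises p to about 0.184, and P(pass) = 1 − 0.816⁵ − 5 × 0.184 × 0.816⁴ = 0.23.

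**4. No drug effect, independent cores (r = 0): chance of passing 2 of 5.** In the pooled ranges, the lower end is the non-surgical layout and the upper end the surgical layout.

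| Specimen CV | Pooled | One fixed pair | Best specimen |
|---|---|---|---|
| 20% | about 0 | 0.05% | 0.2% |
| 31% | 1% | 2% | 7% |
| 42% | 4–7% | 10% | 23% |
| 53% | 10–17% | 19% | 39% |
| 66% | 16–27% | 28% | 52% |

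The effect of the rule itself is the step from fixed pair to best specimen. Pooling also lowers noise, so the step from pooled to best mixes two effects.

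**5. Correlated cores, no drug effect.** At CV 42%, pooled / fixed pair / best is 7–8 / 10 / 19% for r = 0.5 and 8–9 / 10 / 15% for r = 0.8. At CV 31% and r = 0.8, the rule moves the chance from 2% (fixed pair) to 4%.

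**6. Only some participants with two scored cores.** If half have two at CV 42% and r = 0, p = (0.110 + 0.184)/2 = 0.147 and P(pass) = 16%, against 10% with single pairs.

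**7. True 25% reduction, below the 50% threshold, r = 0.** Pooled / fixed pair / best is 2–3 / 5 / 13% at CV 20%, 12–16 / 20 / 41% at CV 31%, and 23–32 / 34 / 59–60% at CV 42%. With r = 0.8 at CV 31% it is 19–20 / 20 / 29%.

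**8. Expansion, 10 evaluable, no drug effect, CV 42%, r = 0.** Expected responses are 10p: 0.7–0.9 pooled, 1.1 with a fixed pair, 1.8 with the best specimen.

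**9. Check without a CV.** Start from a single-pair response probability and take the better of two correlated pairs. The two pairs share one specimen, so their reductions have correlation (1 + r)/2, which is 0.5 at r = 0 and 0.9 at r = 0.8. At p = 0.20, passing rises from 26% to 50% (correlation 0.5) or 37% (0.9). At p = 0.30 it rises from 47% to 73% or 60%. Only perfect agreement between pairs, or a single scored pair, removes the inflation.

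**The case against.** **The rule may never operate.** It is conditional, and collecting two cores is not scoring two. If both cores sit in one block and on one slide, the whole-slide ratio in Section 9.1 already pools them. This stands as a limit on size, but the documents settle neither the block arrangement nor the number scored, and two formalin cores are the planned norm.

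**It is a disclosed choice in a pilot with an openly permissive rule.** That is true, and choosing a signal-seeking analysis in advance is legitimate in itself. The difficulty is what it is used for: naming a lowest effective dose and estimating a response rate.

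**The size is assumed, and independent cores are the unfavourable case.** This is fair. Cores from one biopsy session are plausibly correlated, which shrinks the effect as step 5 shows. With no drug effect, the best-specimen pass probability runs from 0.2% to 52% over the assumed CVs, so no single value can be claimed.

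**It is late to change.** The Amendment 9 update in Section 13.3 says that no cohorts were repeated, so dose assignments already made will stand, and changing the scoring of levels already read is itself post hoc. That argues for reporting both scorings for those levels. It does not argue for leaving best-specimen scoring as the sole basis of the MED.

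**Part of the false-pass risk belongs to the 2-of-5 rule.** Agreed: the fixed-pair column shows that part, and the best-specimen rule adds to it.

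**Conclusion.** The concern holds: the rule is wrong as written for a primary endpoint that names an MED. The direction is certain wherever more than one specimen is scored. A dose becomes more likely to pass, the estimated response rate rises, and the declared MED is pushed toward a lower dose.

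The size is not known. It is zero with one scored specimen per time point and negligible at CV 20% with no drug effect. At CV 42% with no effect, passing rises from 10% to between 15% (core correlation 0.8) and 23% (independent cores). The effect can be larger for a weak but real effect, for example from 20% to 29–41% at CV 31% with a true 25% reduction. These figures rest on log-normal noise, two candidate pairs for every participant, and CVs and correlations that the documents do not supply. This should be fixed; confidence in its practical size is medium.

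**What to change.** Replace the best-specimen sentence in Section 9.1 with wording such as:

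> All adequate formalin specimens at a time point are pooled into one value per participant (sum of positive pixels divided by sum of total pixels), and the 50% rule is applied to that pre/post pair.

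Also:

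- State how many specimens per time point are stained and scored, and fix the adequacy criterion before scoring.
- Add a matching line in Sections 13.4 and 13.8 so that the MED rule and the expansion response rate use the pooled value.
- Label any best-specimen result as exploratory.
- For completed dose levels, re-score on the pooled value where more than one specimen was read, report both results, and state whether any 2-of-5 decision would have differed.
- Optionally, code slide labels for time point and dose, since the documents are silent on reader masking.

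The cost is a short edit plus some re-scoring. The pixel algorithm already yields positive and total counts, so no new tissue or participants are needed if per-specimen counts were kept. Observed response rates may fall, larger cores will carry more weight in the pooled value, and dose assignments already made cannot be undone.

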6.9 Blinding and Unblinding

Not applicable.

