9. CORRELATIVE/SPECIAL STUDIES

9.1 Rationale for Methodology Selection

Gene signature assay: A total of 200ng RNA will be analyzed for the 186-gene liver signature by using nCounter Digital Analyzer system (NanoString) at the UT Southwestern/Simmons Cancer Center shared core facility. A scanned profile with median transcript count <100 will be regarded as having poor quality, and excluded from subsequent analysis. Scanned data will be normalized by scaling the transcript counts with geometric mean of built-in normalization genes by using NanoString normalizer module implemented in GenePattern genomic analysis toolkit (15). Suppression of the 186-gene signature will be quantitatively evaluated for each patient by comparing the paired specimens obtained before and 7 (5-14) days after starting the erlotinib treatment using nearest template prediction algorithm (14) implemented in GenePattern genomic analysis toolkit. A prediction of good prognosis with prediction confidence p-value <0.05 for the day 7 specimen will be regarded as statistically significant suppression of the gene signature in response to the erlotinib treatment.

Assessment of phospho-EGFR staining: Whole slide high-resolution imaging will be performed on the pre-and post-treatment biopsy slides/samples (Aperio, Leica Microsystems Inc. Buffalo Grove, IL 60089 United States). The Positive Pixel Count algorithm will be used quantify the amount of the positive staining on the pEGFR preparation (<http://cancerpreventionnetwork.org/sc.shtml>) three intensity ranges (220-175, 175-100, and 100-0). Only pixels with the strongest intensity (100-0) will be chosen for analysis. Pixels which are stained, but do not fall into the positive-color specification will be considered as negative stained pixels—these pixels will be counted and the fraction of positive pixels to total pixels will be determined. A pseudo-color markup image generated by the algorithm will be examined allowing for confirmation that the desired color and intensity ranges are recorded. Only hepatocytes will

be evaluated and portal tracts will be excluded from analysis. A meaningful reduction in the phospho-EGFR staining is defined as a 50% reduction in positive pixel to total pixel ratio relative to pre-erlotinib baseline.

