10.2.2.2 Surgical Cohort – Post-Intervention

After the liver resection surgery, a portion of the liver specimen that does not contain tumor (≥ 1 cm from negative margin) and consists of at least 1 gram of liver tissue will be placed in RNAlater (Qiagen). One other section of non-tumor bearing liver tissue measuring at least 1 cm x 1 cm x 0.5 cm will be placed in formalin, clearly labeled, and stored in the refrigerator until shipment. The formalin samples will be embedded in paraffin within 24 hours.

Paraffin blocks will be shipped refrigerated to Mayo Clinic (CPN PC Office, address below) for accessioning and then forwarded to the Mayo Clinic PRC in one batch at the end of enrollment for each cohort.

If an institution cannot provide blocks, one 3 mm to 4 mm core should be taken from each block and placed into individual 2 mL tubes. Alternatively, sites may submit ten 5-micron slides plus one H&E.

Notes:

- For institutions that must, based on institutional policies, provide cores or slides instead of paraffin blocks: **Do not create the cores or cut slides until requested to do so by the CPN Pathology Coordinator.**
- Analysis for the study endpoints requires all slides for both time points for all participants to be sectioned at the same time.

The dates and times of collection, paraffin embedding, as well as sectioning will be recorded on the Specimen Submission: Tissue case report form to confirm compliance with these instructions. All samples will be clearly labeled with study number, participant ID, specimen type, and date and time of collection.

Note: Sites are to notify CPN Pathology Coordinator ([name]; [contact]; [contact]) when specimens are shipped for tracking purposes.

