13.2 Randomization/Stratification

Given that this is a single arm pilot trial of erlotinib, there will be no randomization or stratification.

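### The analysis region on each phospho-EGFR slide is chosen with human judgment and no described masking to time point, so a single-arm pre/post comparison cannot separate a reading tilt from drug effect; coding the slides would reduce this cheaply, not remove it.

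*Combined protocol and SAP*

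**What the plan says.** **How the endpoint is read (Section 9.1).** Slides are imaged whole. "The Positive Pixel Count algorithm will be used quantify the amount of the positive staining", and only the strongest intensity band (100-0) is used. Three steps involve a person:

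- Choice of region. Edges tend to stain darker, and "Under the guidance of an Anatomic Pathologist, this artifact is avoided in selecting the analysis region for each slide". The text does not say who draws the region.
- Restriction to hepatocytes, which alone are to "be evaluated and portal tracts will be excluded from analysis".
- Examination of the algorithm's markup image to confirm that the intended color and intensity ranges were recorded.

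A meaningful reduction is "defined as a 50% reduction in positive pixel to total pixel ratio relative to pre-erlotinib baseline".

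**Labels and batching (Section 10.2.2).** "All samples will be clearly labeled with study number, participant ID, specimen type, and date and time of collection". Also, "Analysis for the study endpoints requires all slides for both time points for all participants to be sectioned at the same time". For Cohort B, Section 10.2.2.4 sends baseline and post-intervention blocks to the reading laboratory together, one batch per dose level.

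**Design (Sections 13.2, 7.4.3, 13.8).** "Given that this is a single arm pilot trial of erlotinib, there will be no randomization or stratification". Two responses in the first 5 evaluable participants count as activity at a dose level, and that result decides the next dose or the MED.

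**Masking.** The only entry on blinding is "6.9 Blinding and Unblinding", marked as not applicable, in the pharmaceutical section. Nothing in the supplied text describes coded slides, a random reading order, or regions fixed before the counts are seen.

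**The concern.** The algorithm counts only what falls inside the chosen region. Section 9.1 itself notes that edges stain darker, and the endpoint uses only the darkest band, so including or leaving out marginal tissue acts directly on the counted pixels. The rules given are to avoid edges and to exclude portal tracts. How far in from the edge to start, and how much of the remaining tissue to include, is left open.

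A reader who can see which slide is post-treatment may, without intending it, choose slightly different tissue at the two time points. Every post-intervention slide in this trial comes from a treated participant, so no untreated pair exists against which such a tilt would show. A downward tilt produces responses; an upward one hides them. The documents give no reason to expect either direction. The downward case matters more here because it could pass an inactive dose, and so push the search to lower doses or declare an MED that rests on reading error.

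**Working it through.** **1. The plan's own figure.** Section 13.4 assumes a true response rate of 60% and gives 91% for at least 2 responses in 5.

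P(X ≥ 2) = 1 − (1 − p)^5 − 5p(1 − p)^4. With p = 0.60: 1 − 0.0102 − 0.0768 = 0.913. The figure reproduces. Section 13.4 gives no corresponding probability for an inactive dose.

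**2. Sensitivity of the 2-of-5 rule.** The same formula at assumed rates of spurious response:

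| Spurious response rate per participant | Inactive dose passes |
|---|---|
| 5% | 2.3% |
| 10% | 8.1% |
| 20% | 26.3% |
| 30% | 47.2% |

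Going from 10% to 20% spurious responses roughly triples the chance of a false pass (8.1% to 26.3%).

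**3. A model for a reading tilt (assumption throughout).** Suppose there is no drug effect and each specimen's positive-pixel fraction is log-normal with log-SD s, independently at the two time points. The log of the post/pre ratio then has SD s√2. If region choice multiplies the ratio by m (m = 1 no tilt, m = 0.8 a 20% downward tilt), a response is a ratio of 0.5 or less, so

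p = Φ((−ln 2 − ln m) / (s√2)).

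Worked at s = 0.5, where s√2 = 0.7071:

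- m = 1: Φ(−0.6931 / 0.7071) = Φ(−0.980) = 0.163; P(X ≥ 2 of 5) = 0.190.
- m = 0.9: Φ((−0.6931 + 0.1054) / 0.7071) = Φ(−0.831) = 0.203; P(X ≥ 2 of 5) = 0.269.
- m = 0.8: Φ((−0.6931 + 0.2231) / 0.7071) = Φ(−0.665) = 0.253; P(X ≥ 2 of 5) = 0.374.

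Over a range of s, for a 20% tilt:

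| Log-SD s | Spurious response, no tilt → tilt | Inactive dose passes, no tilt → tilt | Added |
|---|---|---|---|
| 0.3 | 5% → 13% | 2% → 14% | 11 points |
| 0.4 | 11% → 20% | 10% → 27% | 17 points |
| 0.5 | 16% → 25% | 19% → 37% | 18 points |
| 0.7 | 24% → 32% | 35% → 51% | 16 points |

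Smaller tilts do less: at s = 0.5, a 5% tilt gives a pass probability of 23% and a 10% tilt gives 27%, against 19% with none.

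**4. What the model does not show.** The documents give neither the reading variance nor any estimate of tilt. The no-tilt column comes from assumed measurement noise, which coding slides would not change; only the last column bears on masking. Masking also leaves the 91% unchanged.

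**The case against.** The strongest reply is that discretion is narrow. Counting is automated on a fixed intensity band and expressed as a fraction of total pixels. Positive and negative controls are run and both time points are sectioned together. The region sentence describes removing a known artifact, portal-tract exclusion is an anatomical rule, and the markup check is a check on color and intensity rather than a choice of tissue. All of this is true and limits the exposure. It does not close the gap: controls and joint sectioning deal with staining and cutting, not with where pixels are counted.

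A second reply is that the argument rests on silence. That is fair. The laboratory may have a masking procedure outside these documents, and Section 9.1 points to a web page that is not available here. If a procedure exists, a sentence in 9.1 settles the point.

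Four stronger readings are tempting, and the documents do not support them:

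- *That Section 6.9 decides against masked reading.* It sits between registration and agent disposal and is about the study agent. It does not address slide reading.
- *That coding would remove the bias.* In Cohort A the baseline is a biopsy and the post-intervention sample is a resected block of at least 1 × 1 × 0.5 cm (Sections 10.2.2.1 and 10.2.2.2). These can be told apart under any code, and Section 13.4 pools both cohorts in the primary endpoint.
- *That masking would be complete in Cohort B because both samples are biopsies.* The baseline is an archived clinical biopsy from up to 3 months before pre-registration, and the same pathology core has already read slides from it for eligibility (Sections 7.3 and 10.2.2.3). The post-intervention sample is a protocol biopsy (Section 7.7.2). The two may be distinguishable.
- *That coding would also hide dose.* Section 10.2.2.4 batches by dose level, and Section 7.4.3 needs each level's result before the next opens. Slides within a batch share one dose.

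The rule in Section 9.1 to use the specimen with the largest reduction is a separate selection effect, which coding does not touch.

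**Conclusion.** The point holds in limited form. Region selection on the primary endpoint involves human judgment, the documents describe no masking of it to time point, labels reveal the time point, and the design has no comparator that could expose a pre/post reading difference. A reader might infer that the endpoint is known to be biased; nothing in the documents shows that a tilt exists, or how large it would be.

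On the assumed model, a 20% downward tilt would add about 11 to 18 percentage points to the chance that an inactive dose passes, for per-specimen log-SD between 0.3 and 0.7; a 5% or 10% tilt at log-SD 0.5 would add about 4 or 8 points. These figures rest on log-normal, independent readings, no true effect, and a tilt common to all participants. They show that the 2-of-5 rule is sensitive to reading bias; they do not estimate that bias. This is a cheap improvement, not a flaw that invalidates the design.

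**What to change.** In Section 9.1, require the pathology core to:

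1. give the efficacy slides in each batch random codes and a random reading order that hide participant, pairing and time point;
2. select regions by a written rule: all eligible hepatocyte area, with portal tracts and a stated edge margin excluded;
3. lock regions and pixel counts before codes are broken.

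State the limits in the same place: this reduces but does not remove the bias; time-point masking is feasible though not guaranteed in Cohort B and only partial in Cohort A; dose cannot be hidden because specimens are batched by dose level. In Cohort A the written rule and the lock do most of the work.

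The cost is relabelling within a batch that, for Cohort B, already holds both time points. No extra reader is needed, and sample size, eligibility and treatment are unaffected. If the laboratory already does this, describing it in 9.1 is enough.
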